Proteinuria develops in about **30% of kidney transplant recipients** and is **strong predictor of graft loss** (1-3). The amount of proteinuria has a direct correlation with the risk of graft failure (**Figure 1**). More than 80% of patients with proteinuria greater than 1500 mg/d have evidence of allograft glomerular pathology. Among these, transplant glomerulopathy is the leading etiology in about 45% of cases followed by recurrent glomerular disease (25%) (4, 5). Patients with more than 1 gram/day of proteinuria after transplantation carry a dismal prognosis more than 50% of grafts lost after a mean follow up of 5 years (4). The proteinuria on these patients continues to progress and kidney function deteriorates until grafts are lost with no effective therapy to halt this progression, therefore the need to establish novel therapies for this subset of transplant patients.

KDIGO guidelines recommend ACEI/ARB in post-transplant proteinuric patients though there is no clear evidence that this approach improves renal transplant survival (6, 7). In contrary, ACEI/ARB have been associated with significant decrease in renal function, anemia and hyperkalemia post-transplantation. Novel therapies are urgently needed to reduce proteinuria and prevent graft loss in transplant recipients.

It has been recently published that **Abatacept is able to reduce proteinuria in patients with B7-1-positive glomerular disease** by stabilizing β 1-integrin activation in podocytes (8). However, prevalence of positive B7-1 staining in renal allografts and a possible role of B7-1 target therapy in the treatment of proteinuria post-transplantation remains to be explored.

3. Preliminary Data:

[figure not shown]

Figure 1. Risk of graft failure according to degree of proteinuria.

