All study investigators and study staff must follow all appropriate requirements, including Good Clinical Practice (GCP), International Conference on Harmonization (ICH), Code of Federal Regulations (CFR), and the Partners Human Research Committee (PHRC) Institutional Review Board (IRB). The study will be conducted in compliance of the protocol. The protocol, all amendments, and the subject informed consent will receive Institutional Review Board/Independent Ethics Committee (IRB/IEC) approval/favorable opinion before initiation of the study. Study personnel must be qualified by education, training and experience to perform their respective tasks, and will not utilize personnel for whom sanctions have been invoked or where there has been scientific misconduct or fraud.

Appropriate study personnel will obtain signed and dated informed consent from each study participant. [Investigators will ensure that subjects, or their legally acceptable representatives, are clearly and fully informed about the purpose, potential risks, and other critical issues regarding this clinical research study in which they voluntarily participate. The approved consent form will adhere to the ethical principles that have their origin in the Declaration of Helsinki. All relevant safety information regarding the dose/schedule of study drug, or any other drugs/procedures in this clinical study must be explained in the informed consent document. Informed consent will also delineate which authorities may have direct access to study records and documents. Consent will also clearly state that although [name] is the study sponsor, Bristol-Myers Squibb (BMS) is the study funding source and is also supplying study drug for this study.

7. Eligibility:

7.1 Inclusion Criteria:

- Deceased or living donor adult kidney transplant recipients older than 18 years old
- eGFR >30 ml/min
- >6 months after transplantation
- Proteinuria >1 gram/day in spot urine protein/creatinine ratio
- Available biopsy specimen for B7-1 staining at recruitment time.
- Ability to provide written informed consent for the study.
- Must be EBV IgG positive

7.2 Exclusion Criteria:

- Age <18 years
- eGFR<30 ml/min
- Active acute cellular rejection (ACR; higher than borderline) or ACR in the previous 6 months; active acute antibody-mediated rejection.
- Recurrent FSGS
- EBV IgG negative

- Patient on mTOR inhibitor (e.g. Everolimus, Sirolimus)
- Age and Reproductive Status:

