7.5 LESS EFFECTIVE METHODS OF CONTRACEPTION

- Diaphragm with spermicide

- Cervical cap with spermicide
- Vaginal sponge
- Male Condom without spermicide
- Progestin only pills by WOCBP subject or male subject's WOCBP partner
- Female Condom*.

* A male and female condom must not be used together

8. Study Drug: Belatacept (Treatment with Belatacept will continue for 12 months)**:

Belatacept conversion dosing: 5 mg/kg IV on days 1, 15, 29, 43 and 57, followed by an infusion every 28 days thereafter. Calcineurin inhibitors (CNI) Taper: CNI dose will remain the same for week 1 and then will be tapered by 25% each week and discontinued at the end of week 4 (day 29).

Infusion pre-medications: none

Duration of Infusion: 30 minutes

Observation period post-infusion: none

Standard of Care (SOC) Dosing of Belatacept:

5 x the patient's weight (in kg) = mg of Belatacept. Dose then needs to be rounded to the nearest 12.5 mg increment. Example: 74 kg patient x 5 = 370 mg; rounded to the nearest 12.5 mg increment = 375 mg. At the end of 12 months, study subjects have completed the study drug protocol and they have the option to continue on Belatacept treatment, paid for by their medical insurance, or they can switch back to a CNI.

**Please see additional important study drug information on pages 11-12.

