8.2.3.2 Re-Supply

Drug re-supply request form should be submitted electronically or by fax at least 5 business days before the expected delivery date. Deliveries will be made Tuesday through Friday. When assessing need for resupply, institutions should keep in mind the number of vials used per treatment dose, and that shipments may take 14 business days from [BMS or other third-party vendor] receipt of request. Drug is not patient specific. Be sure to check with your pharmacy regarding existing investigational stock to assure optimal use of drug on hand.

9. Study assessments and procedures [Please see: Schedule of Events (SOE) on page 19]:

9A. Belatacept Infusions

See SOE, on page 19, for complete Belatacept infusion schedule.

9A.1 Belatacept Infusion reactions**

In the event of new, serious, and unexpected toxicity potentially related to Belatacept, study drug administration should be interrupted. The investigator must immediately notify the medical monitor (MM). The subject will be considered eligible to receive further study drug treatment only after discussion with the medical monitor.

9B. Early Withdrawal of Study Drug Regimen – safety follow-up schedule:

Subjects in whom Belatacept dosing is discontinued should be placed on a conventional immunosuppressive regimen. To ensure the safety of immunosuppression conversion, repeated blood work for creatinine and drug levels will be performed a 1 week, 2 weeks and 4 weeks post-conversion. A safety follow-up clinic visit 1 month post-conversion will be scheduled.

9C. Study Stopping Rules

Subjects MUST discontinue investigational product (and non-investigational product at the discretion of the investigator) for any of the following reasons:

- Withdrawal of informed consent (subject's decision to withdraw for any reason)
- Any clinical adverse event (AE); abnormal laboratory test results such as refractory neutropenia after immunosuppression adjustment (absolute neutrophil count below 500), refractory life-threatening infection; occurrence of PTLD; refractory acute cellular rejection confirmed by kidney biopsy; or intercurrent illness which, in the opinion of the investigator, indicates that continued participation in the study is not in the best interest of the subject
- Pregnancy
- Loss of ability to freely provide consent through imprisonment or involuntary incarceration for

- treatment of either a psychiatric or physical (e.g., infectious disease) illness

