Study Visits	Screening	Day 1 60 days	Day 15 + 5 days	Day 29 M 1 + 5 days	Day 43 M 2 + 5 days	Day 57 M 3 + 5 days	Day 85 M 4 + 5 days	Day 113 M 5 + 5 days	Day 141 M 6 + 5 days	Day 169 M 7 + 5 days	Day 197 M 8 + 5 days	Day 225 M 9 + 5 days	Day 253 M 10 + 5 days	Day 281 M 11 + 5 days	Day 309 M 12 + 5 days	Day 337 M 13 + 5 days	M18 + 5 days	
Procedures																		
Full Medical History	X																	
Physical Exam	X																	
Vital Signs^a	X	X	X	X	X	X	X	X	X	X	X	X	X	X	X	X		
Chart Review Only																X	X ^f	
Serum or Urine Pregnancy Test (WOCBP only*)	X*																	
EBV Serology^a	X																	
Spot Urine Protein/ Creatinine Ratio^a	X			X			X			X			X			X		
Urine^{a,b}	X			X			X			X			X			X		
Cholesterol Panel^a	X															X		
Serum Glucose^a	X			X			X			X			X			X		
Serum Creatinine^a	X			X			X			X			X			X		
anti-HLA Antibody^c	X ^a															X		
B7-1 biopsy staining^c	X																	
Research Urine^c	X															X		
Research Blood^c	X															X		
Belatacept Infusions^a		X	X	X	X	X	X	X	X	X	X	X	X	X	X	X		
CNI Taper		X ^d	X ^d	X ^e														
AE/SAE Reporting		X	X	X	X	X	X	X	X	X	X	X	X	X	X	X		

KEY:

^aStandard of Care (SOC)

^bUrine = urinalysis w/sediment **AND** Spot Urine = Urine:Creatinine & Urine:Protein; **AND** Urine Protein/Creatinine ratio = calculation needed

^cCentral Lab = send to BWH (transplant research center, [name])

^dCNI dosing to be tapered 25% of baseline dose **PER WEEK** (weekly reduction NOT represented on this SOE), dates of reduction must be documented in eCRFs.

^eLast day of CNI; CNI completely stopped after this day.

^fCollect information about last blood pressure, medications, serum creatinine and urine protein/creatinine

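### No creatinine or urine protein/creatinine is scheduled at Day 1 and baseline is undefined, so the 12-month change endpoints can include drift from before treatment

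*Combined protocol and SAP*

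**What the plan says.** **Schedule of Events.** The "Serum Creatinine^a" row is marked at Screening, Day 29, Day 85, Day 169, Day 253 and Day 337. The superscript denotes standard of care. The spot urine protein/creatinine row has marks in the same columns. Neither row is marked at Day 1 or Day 15, although both are infusion visits. The Day 1 header carries 60 days with no sign or explanation. The Day 29 header reads "Day 29 M 1 + 5 days", and the footnote to that day's taper entry says "CNI completely stopped after this day". Section 8 ends the taper on the same day.

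**Eligibility.** Section 7.1 requires "eGFR >30 ml/min", and the synopsis and Section 7.2 exclude "eGFR<30 ml/min". The synopsis inclusion list admits a value of exactly 30; Section 7.1 does not. No list states how old the qualifying value may be.

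**Endpoints.** Section 11 reports percent change of renal function to 12 months descriptively. The primary endpoint is a reduction in proteinuria of at least 25% over the same period. Both run from baseline, which is not defined.

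**Sampling at conversion.** Section 6 says serum and urine are collected when the patient is converted and again at 12 months. The Schedule of Events puts the research blood and urine at Screening and Day 337.

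**Leaving belatacept.** Section 9B covers early discontinuation: "To ensure the safety of immunosuppression conversion, repeated blood work for creatinine and drug levels will be performed" at 1, 2 and 4 weeks.

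**The concern.** A change endpoint should start from a value taken as close to the start of treatment as is practical. Here the only scheduled pre-treatment creatinine is the screening one, and its age at the first infusion is not clearly limited. The direction of drift is not neutral in this population. Section 2 says of these patients: "The proteinuria on these patients continues to progress and kidney function deteriorates until grafts are lost". Kidney function lost between Screening and Day 1 would therefore be recorded as loss on belatacept.

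The same gap affects the primary endpoint. Proteinuria that rises before Day 1 would count against the 25% reduction. In the other direction, the only scheduled pre-treatment proteinuria value is also the one that qualified the patient at about 1 g/day, so some fall on re-measurement is expected from selection alone. The documents do not allow the net effect on proteinuria to be sized.

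**Working it through.** **Checking the table columns.** The table was extracted from a PDF, so the columns need checking first. Section 8 doses on days 1, 15, 29, 43 and 57 and then every 28 days. Continuing that rule gives 85, 113, 141, 169, 197, 225, 253, 281, 309 and 337. These are exactly the visit days in the schedule, 15 infusions in all, and each has a mark in the infusion row. The creatinine marks can therefore be placed with confidence.

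**Gap between scheduled values.** Inputs: 60 days (Day 1 header, read as the longest screening interval); Day 1 to Day 29 = 28 days; visit window +5 days.

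- Screening to Day 29: 60 + 28 = 88 days; with the window, 88 + 5 = 93 days.
- With a Day 1 value added: 28 days; with the window, 28 + 5 = 33 days.
- Age of the baseline at first infusion: up to 60 days now, 0 with a Day 1 value.

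**Size of the drift.** The documents give no eGFR slope, so the slopes below are assumptions. Loss over the interval = slope × 60/365.25. As a share of the starting value = loss/eGFR × 100.

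| Assumed loss (ml/min/year) | Loss in 60 days (ml/min) | % of eGFR 30 | % of eGFR 45 |
|---|---|---|---|
| 2 | 0.33 | 1.1 | 0.7 |
| 5 | 0.82 | 2.7 | 1.8 |
| 10 | 1.64 | 5.5 | 3.7 |
| 20 | 3.29 | 11.0 | 7.3 |

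The loss is proportional to the interval: a 30-day screening period halves every entry.

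**How it enters the endpoint.** Let S be the screening value, D the Day 1 value and E the value at 12 months. Change from screening is (E − S)/S; change from Day 1 is (E − D)/D. Suppose function is completely stable after Day 1, so that E = D. The change from Day 1 is then 0, while the change from screening is −(S − D)/S, which is the percentage in the table. A patient screened at 45 and losing 10 ml/min/year beforehand would be recorded as −3.7% although nothing was lost on treatment.

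**The case against.** **The 60 days is inferred.** It rests on an unsigned fragment in a table header, and even if read correctly it is a maximum. This stands. The missing Day 1 value and the undefined baseline do not depend on it; the 88 and 93 days and the table do.

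**A baseline exists.** A reader might infer that renal function has no baseline. The documents do not support that: the screening creatinine precedes any belatacept or taper and can serve. The defect is that it is not tied to conversion and not named.

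**Section 6 promises a sample at conversion.** That paragraph concerns stored research samples and does not name creatinine, and the schedule puts those draws at Screening. It does not close the gap; the two places need reconciling.

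**Ineligible patients would be treated.** A reader might infer this, for example with a fall from 31 to 27 before Day 1. That is 4 ml/min in 60 days, or 4 × 365.25/60 ≈ 24 ml/min/year, above every slope assumed here. Even falling from 31 to 30 needs about 6.1 ml/min/year over the full 60 days. Nor does any section say that the limit must hold on Day 1; assessing eligibility at screening is ordinary, and local standard-of-care values may exist although none is required at Day 1.

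**The next value comes after withdrawal.** A reader might infer that the inhibitor is already gone by the next creatinine. Day 29 is its last day, so the value falls at the end of the taper.

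**Section 9B contradicts the schedule.** It covers a different situation, early discontinuation of belatacept, and pairs creatinine with drug levels. The planned conversion begins with a week at full inhibitor dose and then a taper. The two schedules differ, and 9B gives conversion safety as its reason, so the sponsor should explain the difference. It is not a strict contradiction.

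**The renal endpoint is secondary and descriptive.** True, and no test depends on it. But the primary endpoint has the same schedule.

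**Conclusion.** The point holds as a matter of measurement timing and definition. No creatinine or urine protein/creatinine is scheduled between Screening and Day 29, the permitted age of the qualifying value is not stated in words, and baseline is undefined for both change endpoints. If the header means a 60-day interval, and if eGFR falls by 2 to 20 ml/min/year, the renal-function change for a patient at an eGFR of 30 can be off by about 1% to 11%, and by proportionately less with a higher eGFR or a shorter screening period. With slow decline the effect is small. Sample size and power are unaffected. This is an inexpensive improvement. It does not show that the trial is invalid or that patients are dosed outside the criteria.

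**What to change.** 1. Add a pre-infusion serum creatinine and spot urine protein/creatinine ratio to the Day 1 column of the Schedule of Events.
2. In Section 11, name the Day 1 values as the baseline for percent change of renal function and for the 25% reduction in proteinuria, and repeat both analyses with the screening value as a sensitivity baseline.
3. State in words what the 60 days in the Day 1 header means.
4. Reconcile Section 6, which places sampling at conversion, with the schedule, which places it at Screening.
5. Ask the sponsor to reconcile the eGFR limits in the synopsis and Sections 7.1 and 7.2, the timing of creatinine in the schedule, and the creatinine schedule in Section 9B. The clinical content is for the sponsor to decide; no pre-dose rule is proposed here.

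The cost is one additional routine blood and urine sample per patient at a visit already held, and wording changes in the schedule and Section 11.
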